### 4.2.2.1. On-Treatment Adherence

The level of on-treatment adherence to the study drug regimen will be determined by the total amount of study drug administered relative to the total amount of study drug expected to be administered during a subject's actual on-treatment period based on the study drug regimen.

The level of on-treatment adherence will be expressed as a percentage using the following formula:

$$\text{On-Treatment Adherence (\%)} = \left( \frac{\text{Total Amount of Study Drug Administered}}{\text{Study Drug Expected to be Administered on Treatment}} \right) \times 100$$

If the calculated on-treatment adherence is > 100%, it will be set to 100%. Descriptive statistics for the level of on-treatment adherence with the number and percentage of subjects belonging to adherence categories (eg, < 80%, ≥ 80% to < 90%, ≥ 90%) will be provided by treatment group for the Safety Analysis Set.

No formal statistical testing is planned.

A by-subject listing of study drug administration and drug accountability will be provided by subject ID number (in ascending order) and visit (in chronological order).

#### **4.3. Protocol Deviations**

Subjects who did not meet the eligibility criteria for study entry, but enrolled in the study will be summarized regardless of whether they were exempted by the sponsor or not. The summary will present the number and percentage of subjects who did not meet at least 1 eligibility criterion and the number of subjects who did not meet specific criteria by treatment group and overall based on the All Randomized Analysis Set. A by-subject listing will be provided for those subjects who did not meet at least 1 eligibility (inclusion or exclusion) criterion. The listing will present the eligibility criterion (or criteria if more than 1 deviation) that subjects did not meet and related comments, if collected.

Protocol deviations occurring after subjects entered the study are documented during routine monitoring. The number and percentage of subjects with important protocol deviations by deviation category (eg, eligibility criteria, informed consent) will be summarized by treatment group and overall for the All Randomized Analysis Set. A by-subject listing will be provided for those subjects with any important protocol deviation.

A by-subject listing will be provided for subjects with important protocol deviations related to COVID-19. A separate listing will be provided for subjects with non-important protocol deviations related to COVID-19.

#### **4.4. Missed and Virtual Visits due to COVID-19**

A by-subject listing of subjects with missed or virtual visits due to COVID-19 will be provided by subject ID number in ascending order.

Information regarding missed or virtual visits due to COVID-19 was collected as free text in the CRF comment fields. The determination of missing or virtual visits due to COVID-19 was done using Natural Language Processing (NLP) to search the CRF comment fields. A detailed explanation of the algorithm is provided in [Appendix 12](#).

## 5. BASELINE CHARACTERISTICS

### 5.1. Demographics and Other Baseline Characteristics

Subject demographic variables and other baseline characteristics will be summarized by treatment group and overall using descriptive statistics for continuous variables, and using the number and percentage of subjects for categorical variables. The summary of demographic data will be provided for the Safety Analysis Set.

- Age (years, on the date of first dose of the study drug)
- Age group (< 65 years,  $\geq$  65 years)
- Sex at birth (female, male)
- Race
- Ethnicity (Hispanic or Latino, Not Hispanic or Latino)
- Geographic region (United States [US], non-US)
- Weight (in kg)
- Height (in cm)
- Body mass index (BMI; in kg/m^2)
- Smoking status (former, current, never)

A by-subject demographic listing, including the informed consent date, will be provided by subject ID number in ascending order.

### 5.2. Baseline Disease Characteristics

Stratification factors (listed in Section 3.3) and other baseline disease characteristics listed below will be summarized for the Safety Analysis Set by the same method as demographic tables, using descriptive statistics for continuous variables and using number and percentage of subjects for categorical variables.

- Duration of perianal fistulizing CD (years) from date of diagnosis to first dosing date of study drug
- Duration of perianal fistulizing CD group (< 1 year,  $\geq$  1 to  $<$  3 years,  $\geq$  3 to  $<$  7 years,  $\geq$  7 years)

- Location of CD: ileal, colonic, ileocolonic and isolated upper disease
- [Redacted]
- Active Luminal Disease (CDAI  $\geq 150$ )
- Moderately Active Luminal Disease (CDAI  $\geq 220$ )
- Baseline Proctitis SES-CD score (sum of size of ulcers and ulcerated surface for the rectum and anal canal segments)
- Baseline Anal Canal SES-CD score (sum of size of ulcers and ulcerated surface for the anal canal segment)
- Presence of Moderately to Severely Active Proctitis (yes, no)

- Number of Draining Perianal Fistula at Baseline
- Anatomy of draining perianal fistulae at screening determined by MRI (simple vs complex)
- History of complications of perianal CD
  - Anal stenosis (yes, no)
  - Perirectal / perianal abscess (yes, no)
- Perianal Fistulizing CD treatment history
  - Prior use of antibiotics (yes, no)
  - Prior use of immunomodulators (yes, no)
  - Prior use of TNF $\alpha$  antagonist as listed in [Appendix 2](#) (yes, no); and for subjects with prior use:
    - Number of TNF $\alpha$  antagonists used
      - 1
      - 2
      - $\geq 3$

- Worst outcome of prior use of TNF $\alpha$  antagonist
  - Treatment failure
  - Intolerance, including both allergic and non-allergic intolerance
  - Other
- Other CD treatment history
  - Prior use of systemic corticosteroids (yes, no)
  - Number of prior exposure to biologic agent for CD as listed in [Appendix 3](#) (0, 1, 2,  $\geq 3$ )
  - Prior use of vedolizumab (yes, no); and for subjects with prior use:
    - Worst outcome of prior use of vedolizumab
      - Treatment failure
      - Intolerance, including both allergic and non-allergic intolerance
      - Other
    - Prior use of ustekinumab (yes, no) and for subjects with prior use:
      - Worst outcome of prior use of ustekinumab
        - Treatment failure
        - Intolerance, including both allergic and non-allergic intolerance
        - Other

**Note:** The worst outcome of a prior treatment is treatment failure, followed by intolerance, and then other outcomes.

- Concomitant CD treatment
  - Antibiotic treatment for fistulizing CD at Baseline (yes, no)
  - Concomitant use of vedolizumab at Day 1 (yes, no)

- Concomitant use of systematically absorbed corticosteroids and immunomodulators
  - Systematically absorbed corticosteroids only
  - Immunomodulator only
  - Both systematically absorbed corticosteroids and immunomodulator
  - Neither
- Prednisone equivalent dose for subjects who were on systematically absorbed corticosteroids at baseline (mg/day)
- Prednisone equivalent dose for subjects who were on systematically absorbed corticosteroids at baseline (> 0 to 10 mg/day, > 10 to 20 mg/day, > 20 mg/day)
- 5-aminosalicylates (yes, no)

A by-subject listing of the above baseline characteristics will be provided by subject ID number in ascending order.

### **5.3. Medical History**

Medical history (disease-specific and general conditions) and IBD family history data will be collected at screening and presented in data listings.

General medical history data will be coded using the current version of Medical Dictionary for Regulatory Activities (MedDRA).

## 6. EFFICACY ANALYSES

### 6.1. General Considerations

The efficacy analysis will be conducted on the FAS, defined in Section 3.1.2, unless otherwise specified. No formal hypothesis testing will be performed.

The definitions of selected efficacy endpoints are provided in [Table 6-1](#). [Appendix 10](#) and [Appendix 11](#) include detailed definition of study treatment failure and the corresponding data handling rules for efficacy analysis.

**Table 6-1. Definitions of Selected Efficacy Endpoints**

Type	Endpoint	Definition
Primary	Combined fistula response at Week 24	Reduction of $\geq 1$ from baseline in the number of draining external perianal fistula openings that were present at baseline, and absence of fluid collections $> 1\text{cm}$ on MRI pelvis at Week 24, among subjects with at least 1 draining external perianal fistula opening at baseline
Secondary	Combined fistula remission at Week 24	Perianal fistula closure of all external openings that were draining at baseline, and absence of fluid collections $> 1\text{cm}$ on MRI pelvis at Week 24, among subjects with at least 1 draining external perianal fistula opening at baseline
Secondary	Time to clinical fistula response	The time interval in days from date of first dosing of study drug to the first observation (during scheduled or unscheduled clinical visits) when $\geq 1$ of the draining external perianal fistula openings that were present at baseline achieves perianal fistula closure, among subjects with at least 1 draining external perianal fistula opening at baseline. Subjects not known to have a clinical fistula response will have their clinical fistula response time censored at the last time that lack of clinical fistula response was documented.

Type	Endpoint	Definition
Secondary	Time to clinical fistula remission	The time interval in days from date of first dosing of study drug to the first observation (during scheduled or unscheduled clinical visits) of perianal fistula closure of all external openings that were draining at baseline, among subjects with at least 1 draining external perianal fistula opening at baseline. Subjects not known to have a clinical fistula remission will have their clinical fistula remission time censored at the last time that lack of clinical fistula remission was documented.
Secondary	Proctitis remission at Week 24, in subjects that had moderately to severely active proctitis at baseline	A Proctitis SES-CD Score (sum of ulcer size and ulcerated surface SES-CD endoscopy subscores for the rectum and anal canal) of 0 assessed by centrally read flexible sigmoidoscopy at Week 24, in subjects that had moderately to severely active proctitis at baseline
		CCI
		CCI

### Summary of Dichotomous Efficacy Endpoints

Numbers and percentages of subjects achieving each of the dichotomous efficacy endpoints defined in [Table 6-1](#), and numbers and percentages of subjects not achieving those endpoints for the following reasons will be summarized by treatment, in a hierarchy order with the first reason being the highest.

- 1) Subjects who do not meet the endpoint based on observed data
- 2) Subjects who do not meet the endpoint due to study treatment failure

CCI

CCI

- 5) Subjects who do not meet the endpoint due to study drug discontinuation led by protocol-specified disease worsening
- 6) Subjects who do not have sufficient measurements to determine the endpoint due to study drug discontinuation for other reasons
- 7) Subjects who do not have sufficient measurements to determine the endpoint due to other reasons

#### **Non-responder Imputation**

For analysis of binary efficacy endpoints defined in [Table 6-1](#), subjects who do not have sufficient measurements due to any reason (including treatment failures and CDAI or PDAI non-responders at Week 10) to determine the endpoint will be considered not meeting the endpoint (ie, non-responder imputation [NRI]).

CCI

CCI

CCI

#### **6.1.2. Calculation of Segmental SES-CD Scores**

Proctitis SES-CD score (which includes an overall assessment of both rectum and anal canal segments) and Anal Canal Segmental SES-CD score will be calculated at Screening (used as baseline) and Week 24 visit (or early termination, if applicable). Only size of ulcers and ulcerated surface variables will be included for the calculation of these scores (see [Appendix 6](#)).

## **6.2. Primary Efficacy Endpoint**

### **6.2.1. Definition of the Primary Efficacy Endpoint**

The primary efficacy endpoint is the combined fistula response at Week 24. Please refer to [Table 6-1](#) in Section [6.1](#) for the endpoint definition.

### **6.2.2. Analysis of the Primary Efficacy Endpoint**

The number and proportion of subjects establishing combined fistula response at Week 24 for each treatment group will be summarized with corresponding 90% exact CI by Clopper-Pearson method. The difference in proportions between each filgotinib dose group and the placebo group will be presented along with the associated 90% CI. No formal hypothesis testing will be performed.

For subjects who completed the Week 24 visit, the following missing value imputation will be used before deriving the proportion of subjects establishing combined fistula response at Week 24:

- If the clinical fistula assessment data is missing at Week 24, then the number of draining external perianal fistula openings at Week 24 will be imputed by Last Observation Carried Forward (LOCF) method using the number of draining external perianal fistulae openings from the last available scheduled or unscheduled visit, among draining external perianal fistulae openings at baseline only.
- If the MRI data is missing at Week 24, then absence of fluid collection > 1 cm will be imputed based on whether there was an absence of fluid collection > 1 cm at baseline (Yes, No), which will be derived from the size of fluid collections at baseline from the Total Fistula Score CRFs.

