Diagnostic modalities for fistulizing CD have improved over the last decade. An accurate assessment of each fistula's anatomy before treatment is essential, and enables the physician to choose the most appropriate therapy. Inadequate characterization of the fistula and associated pathology can result in potentially poor clinical outcomes. MRI is now considered the gold standard imaging tool to evaluate the perianal complication of CD as it offers excellent soft tissue discrimination with a wide field of view and it carries no radiation hazard {[Gecse 2004](#)}. Previous studies have shown that MRI is particularly sensitive for the detection of pelvic abscesses in CD patients, even in the absence of clinical signs {[Luniss 1994, Myhr 1994](#)}. Use of MRI as preinclusion clinical evaluation will ensure accurate characterization of the fistulæ and detect any abscess which may require drainage.

[figure not shown]
With the advent of anti-TNF therapy, the goal of treatment for fistulizing CD has evolved from symptomatic improvement (eg, by drainage) of the fistula to complete cessation of drainage and, in some patients, fistula closure and fibrosis of the fistula tract {[Gecse 2004](#)}. However, the optimal clinical index for assessing perianal CD is still under debate. Even though the endpoint adopted in previous trials in perianal fistulizing CD (ie, disappearance of drainage from at least 50% of the fistulae) {[Present 1999, Sands 2004](#)} is clinically relevant, it has been shown that cessation of drainage from external orifices does not accurately reflect what is happening to the fistula track. A small prospective cohort study including 18 subjects with perianal CD showed that persistent inflammatory activity in the fistula track is observed even after long-term (46 weeks) infliximab therapy, whereas external orifices are observed to heal and to stop draining rapidly after the therapy {[Van Assche 2003](#)}. A primary endpoint at 6 months into the treatment course was chosen to allow healing of the fistulae.

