8.5. Efficacy Analysis

8.5.1. Primary Analysis

The number and proportion of subjects establishing combined fistula response at Week 24 for each treatment group will be summarized with corresponding exact 90% CI based on binomial distribution (Clopper-Pearson method). The difference in proportions between each filgotinib dose group and the placebo group will be presented along with the associated 90% CI. Subjects who do not have sufficient measurements to determine efficacy endpoint will be considered failures (ie, non-responder imputation [NRI]). No formal hypothesis testing will be performed.

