8.5.2. Secondary Analyses

The same summaries used for the primary endpoint will be utilized for the proportion of subjects establishing combined fistula remission at Week 24. Subjects who do not have sufficient measurements to determine efficacy endpoint will be considered failures (ie, NRI).

For time-to-event secondary endpoints, the summary statistics (eg, median, Q1, Q3) from the Kaplan-Meier method will be provided for each treatment group. The stratified Cox proportional hazards model will be used to estimate the hazard ratio with the corresponding 90% CI.

CCl [REDACTED]

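### SAP 6.2.2 fills a missing Week 24 MRI with the pre-treatment scan result, so a Week 24 completer the protocol counts as a failure can become a combined fistula responder

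*SAP*

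**What the plan says.** **Protocol.** Section 8.5.1 gives one rule for missing primary endpoint data: "Subjects who do not have sufficient measurements to determine efficacy endpoint will be considered failures (ie, non-responder imputation [NRI". Section 8.5.2 repeats it for combined fistula remission, and the synopsis agrees. None of these makes an exception for subjects who attend Week 24.

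**SAP, general rule.** The NRI paragraph in Section 6.1 covers the binary endpoints of Table 6-1. It treats "subjects who do not have sufficient measurements due to any reason" as not meeting the endpoint. Table 6-1 requires absence of a collection larger than 1 cm "on MRI pelvis at Week 24, among subjects with at least 1 draining external perianal fistula opening at baseline".

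**SAP, primary analysis.** Section 6.2.2 adds a prior step: "For subjects who completed the Week 24 visit, the following missing value imputation will be used before deriving the proportion". A missing drainage count "will be imputed by Last Observation Carried Forward (LOCF) method". For the scan, "If the MRI data is missing at Week 24, then absence of fluid collection > 1 cm will be imputed based on" whether such a collection was absent at baseline.

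**Reach and limits.** SAP 6.3.2 analyses the binary secondary endpoints by the primary method, so the rule appears to extend to combined remission. The treatment-failure rules in SAP Appendix 11 override it. Subjects who did not complete Week 24 remain under NRI. For proctitis remission, SAP 6.3.2 does the opposite: a missing Week 24 score is not imputed and the subject is a non-responder.

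**The concern.** The endpoint has two components, drainage and MRI, and both are required. The SAP lets the MRI component be met by a scan taken before the first dose. That scan says nothing about collections that form on treatment, so an affected subject is judged on drainage alone.

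Protocol 1.3 explains why drainage alone was thought insufficient: "cessation of drainage from external orifices does not accurately reflect what is happening to the fistula track". It adds that a hidden pelvic abscess may show itself only once the external openings stop draining. The imputation thus assumes no new collection in the very subjects, clinical responders, whom the scan was meant to check.

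The trial tests no hypothesis. The arm rates, their differences from placebo and the 90% CIs are its result, and with 15 placebo subjects one or two reclassifications visibly change them.

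**Working it through.** **1. The plan's own precision figures.** Clopper-Pearson 90% limits for x responders of n are Beta(0.05; x, n−x+1) and Beta(0.95; x+1, n−x). For 12/30 this gives 24.95% to 56.61%, matching the 25% and 57% in Protocol Table 8-1 (SAP Table 1-1). All seven rows reproduce. The table covers n = 30 only and makes no allowance for missing data.

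**2. One subject under each document.** Take a Week 24 completer with one fewer draining opening, no baseline collection above 1 cm, no treatment failure and no Week 24 MRI.
- Protocol 8.5.1: the endpoint cannot be determined, so failure.
- SAP 6.2.2: MRI component imputed as met and drainage component met, so responder.

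If the Week 24 drainage count is also missing, the subject can respond with neither component measured at Week 24. A subject with a baseline collection above 1 cm stays a non-responder under both.

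**3. Age of the substituted data** (Protocol 6.6 and Appendix 2: MRI at screening, Week 24 and early termination only).
- Scan on Day −1: 1 + 168 = 169 days before Day 169.
- Scan on Day −30: 30 + 168 = 198 days.
- Drainage: the last scheduled assessment before Week 24 is Week 18, 169 − 127 = 42 days earlier. It is at least on treatment, so this is the lesser issue.

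These are nominal intervals; Protocol 6.11.2 allows later randomization with permission.

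**4. Effect of one reclassified subject.** Filgotinib arm: 1/30 = 3.3 points. Placebo arm: 1/15 = 6.7 points.

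**5. Expected rise in an arm over NRI.**

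Rise = P(completes Week 24) × P(MRI missing, given completion) × P(clinical response) × P(no baseline collection > 1 cm)

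The documents give none of these terms. Assumed ranges: 5–20% missing, 30–50% response, 70–90% without a collection.
- All complete: 0.05 × 0.30 × 0.70 = 1.05 points, up to 0.20 × 0.50 × 0.90 = 9.0 points.
- 70% complete: 0.7 × 1.05 = 0.7 points, up to 0.7 × 9.0 = 6.3 points.
- Middle case: 0.7 × 0.10 × 0.40 × 0.80 = 2.24 points, or 0.67 subjects per filgotinib arm and 0.34 on placebo.

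The drainage LOCF is not included.

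**6. Effect on the difference from placebo.** Responder counts are assumed, starting from 12/30 against 3/15 under NRI.

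| Imputed responders | Filgotinib (90% CI) | Placebo (90% CI) | Difference |
|---|---|---|---|
| None | 40.0% (25.0–56.6) | 20.0% (5.7–44.0) | 20.0 |
| 2 filgotinib | 46.7% (30.8–63.0) | 20.0% (5.7–44.0) | 26.7 |
| 1 placebo | 40.0% (25.0–56.6) | 26.7% (9.7–51.1) | 13.3 |
| 2 placebo | 40.0% (25.0–56.6) | 33.3% (14.2–57.7) | 6.7 |

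**The case against.** - **The rule is disclosed.** SAP 3.5.1 points to 6.2.2 for missing fistula and MRI data, and the revision table records the MRI rule as added in Version 2. That stands: it is not hidden. But the stated reason is clarification, and nothing visible identifies it as a departure from Protocol 8.5.1.
- **The SAP can be read consistently:** impute first, then apply NRI to whatever is still undetermined. This also stands, so the conflict is with the protocol rather than within the SAP. That order is, however, exactly how the protocol's rule is pre-empted.
- **Redaction.** Much of SAP Section 6 after 6.3.2 is blacked out. A declared change or an NRI sensitivity analysis may be there, so its absence cannot be asserted.
- **The illustration is harsher than the model.** In the middle case, and with subjects independent, two or more imputed placebo responders have probability 1 − 0.9776^15 − 15 × 0.0224 × 0.9776^14 = 1 − 0.712 − 0.245 ≈ 0.04. Even at 9.0 points the expected placebo number is 15 × 0.09 = 1.35. The fall to 6.7 points shows sensitivity and is not a forecast.
- **Scans may seldom be missing.** Entry requires willingness to have MRI, the Week 24 scan may be done up to 14 days early, and the completers' extension option is tied to it. The 20% upper end has no source. Against this, SAP 3.8 and 4.4 provide for missed and virtual visits during COVID-19.
- **The rationale is stretched.** The Protocol 1.3 sentence quoted above concerns inflammation in the track, which the 1 cm criterion does not measure. Fair; the hidden-abscess argument in the same section is the closer support.
- **NRI misclassifies too.** A true responder who misses only the scan becomes a failure. True, but the protocol chose that rule.

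**Conclusion.** The concern holds. For Week 24 completers, SAP 6.2.2 replaces the protocol's failure rule with an imputation that can make a responder of someone who has no Week 24 MRI, on an endpoint defined by MRI at that visit. The contradiction follows from the wording and does not depend on any assumed rate.

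The size does depend on assumptions: an expected rise of 0.7 to 9.0 points in an arm, 2.2 in the middle case, with every input assumed. The direction within an arm is fixed, since the rate can only rise relative to NRI. The direction for the difference is not fixed, because it depends on which arm has the missing scans. In a small descriptive trial this should be fixed before the results are produced.

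**What to change.** In SAP 6.2.2, and for combined remission in 6.3.2, state for the main analysis: *Subjects without a Week 24 MRI or without a Week 24 drainage assessment are non-responders (Protocol 8.5.1, 8.5.2).* In addition:

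- Keep the baseline-MRI and LOCF version as a labelled sensitivity analysis.
- Define what counts as completing the Week 24 visit, including whether a virtual visit qualifies.
- Report per arm how many subjects were imputed for MRI, for drainage and for both.

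If the sponsor prefers to keep the imputation as the main analysis, the SAP should declare it as a change from the protocol and show the NRI result beside it. If redacted text already does this, a cross-reference from 6.2.2 is enough for that part.

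The cost is SAP wording and one extra output. The downside is slightly lower reported response rates, because a true responder who missed only the scan counts as a failure in the main analysis.
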